7.4 Follow-up Period

The follow-up period begins 6 hours after the last dose of study drug (96 hours from initial dose for subjects completing the full course of treatment) or time of delivery if sooner and continues until 6 weeks (± 1 week) postpartum for the mother and until 36 weeks (± 1 week) corrected gestational age for the infant. If delivery occurs during the initial 24 hours of follow-up, every attempt should be made to complete applicable follow-up assessments at least once prior to delivery.

The following assessments will be conducted during the follow-up period.

Other than where specific timepoints are noted below, assessments will be conducted per standard of care during the follow-up period. For study purposes, standard of care assessments will not be captured unless there are clinical findings. If the time windows for assessments overlap (e.g., 24 hours postpartum occurs within an hour of 24 hours post final dose), then only the last set of assessments should be captured.

- Biophysical profile – should be completed 6 hours (± 2 hours) after final dose and then per standard of care until delivery.
- Weight – should be collected 6 hours (± 2 hours) after final dose, 24 hours postpartum (± 6 hours), up to 24 hours prior to discharge, and at 6 weeks postpartum (if visit conducted in the clinic).
- Mental status exam, brief physical examination, laboratory assessments (clinical chemistry, hematology, and urinalysis), preeclampsia symptom assessment, and MEOWS – should be

- collected 24 hours (\pm 4 hours) after final dose, 24 hours postpartum (\pm 6 hours), up to 24 hours prior to discharge, and at 6 weeks postpartum (if visit conducted in the clinic).
- ECG – completed per standard of care.
 - Fetal heart rate monitoring – completed per standard of care. Clinically significant abnormal findings along with category designation (e.g., III) from fetal heart rate monitoring must be recorded.
 - A full set of vital signs (i.e., blood pressure and heart rate, respiratory rate, body temperature, and pulse oximetry) – should be collected 24 hours (\pm 4 hours) post final dose and then once a day until discharge, and at 6 weeks postpartum. If possible, vital signs should be collected in the morning.
 - One blood sample should be collected around the time of delivery for PK analysis.
 - Maternal outcome assessments will be completed 24 hours postpartum (\pm 6 hours) and up to 24 hours prior to discharge and will include:
 - Delivery data
 - Anti-hypertensive use
 - Use of assisted ventilation
 - Treatment with non-red cell blood products
 - Length of hospital stay
 - Blood sample for immunogenicity analysis will be collected at the 6-week postpartum visit (if visit conducted in the clinic).
 - Concomitant medication record will be collected until discharge. Additional information regarding anti-hypertensive medications and opioid medications should be collected through the 6-week postpartum visit.
 - Adverse event record – will be collected until discharge and at 6 weeks postpartum (via clinic visit or phone). If no adverse events are identified that require follow-up for a given subject, then that subject's participation is considered completed and the subject will be discharged from the study. If AEs are identified that require follow-up, arrangements should be made with the subject to follow-up by phone or in person until the AEs are resolved or considered stable, at which time the study will be considered completed for that subject.

Subjects may be contacted in the future to obtain long term follow-up information about the mother and infant.

7.5 Infant Assessments

The following assessments will be conducted for the infant. For study purposes, standard of care assessments will not be captured unless there are clinical findings.

- If cord blood is available, a cord blood sample will be collected for the following assessments:
 - Arterial cord gas pH and base excess/base deficit
 - Analysis of AMAG-423 concentration
- Infant physical examination and laboratory assessments (clinical chemistry and hematology) – standard of care until 36 weeks (\pm 1 week) corrected gestational age.
- Blood sample for immunogenicity analysis will be collected at 36 weeks (\pm 1 week) corrected gestational age.
- Infant cranial ultrasound – Day 7 (\pm 1 day) and at 36 weeks (\pm 1 week) corrected gestational age.
 - Cranial ultrasounds should be performed per existing medical practice imaging process standards. Cranial ultrasounds will be recorded for review by a central

radiologist to confirm if IVH is present, and if so, grade of IVH. Cranial ultrasound collection and review procedures will be detailed in a separate document.

- Status at birth
 - Apgar scores at 1 and 5 minutes post birth
 - Apgar score at 10 minutes post birth, if available
- Infant exam (weight, length, head circumference)
- The infant outcome assessment will be completed at birth and at 36 weeks (\pm 1 week) corrected gestational age and will include:
 - Neonatal intensive care unit (NICU) stay
 - Ventilator use and duration
 - Continuous positive airway pressure (CPAP) / high flow nasal cannula (HFNC) use and duration
 - Status at 36 weeks (\pm 1 week) corrected gestational age (i.e., alive or expired, hospitalized or discharged).
- Blood transfusion receipt and any available related information (e.g., hemoglobin and hematocrit levels prior to transfusion and within 24 hours of transfusion, and nothing by mouth (NPO) status)
- Medical complications including:
 - Patent ductus arteriosus (PDA) – documentation regarding details of PDA condition and treatment should also be captured.
 - Respiratory distress syndrome
 - NEC ([Appendix 6](#))
 - Retinopathy of prematurity, including stage
 - Bronchopulmonary dysplasia
 - Hypoxic ischemic encephalopathy
 - IVH, including grade ([Appendix 7](#))
 - Cystic periventricular leukomalacia
 - Sepsis, early and late onset
 - Previously unrecognized anomalies (e.g., including, but not limited to, atrial septal defect [ASD] and ventricular septal defect [VSD]).
 - Other conditions of prematurity as outlined in [Appendix 4](#)
- Concomitant medication record will be collected until 36 weeks (\pm 1 week) corrected gestational age.
- Adverse event record – Will be collected until 36 weeks (\pm 1 week) corrected gestational age. If no adverse events are identified that require follow-up for a given subject, then that subject's participation is considered completed and the subject will be discharged from the study. If AEs are identified that require follow-up, arrangements should be made to follow-up by phone or in person until the AEs are resolved or considered stable, at which time the study will be considered completed for that subject.

7.6 Placental and Umbilical Cord Assessment

If a pathological examination of the placenta is considered part of standard of care, analysis will be conducted by the clinical site pathology department. If conducted, information obtained during the evaluation will be collected in the CRF.

Optional Assessments (US sites only)

A true cut biopsy of the placenta (measuring approximately 1 cm x 1 cm) will be collected for future analysis of Na^+/K^+ -ATPase activity. The sample should be collected close to the insertion of the umbilical cord.

An approximately 3 cm length of umbilical cord will be collected for future analysis of Na^+/K^+ -ATPase activity.

Placenta and umbilical cord samples will be collected, prepared, stored, and shipped according to sampling instructions that will be provided separately.

7.7 Assessment Windows

Every effort will be made to collect AMAG-423 PK samples at the time point specified; however, the actual collection times may deviate by:

- ± 5 minutes at the end of infusion;
- ± 15 minutes from the 3-hour and 6-hour time points;
- - 15 minutes for pre-dose time points

A full set of vital signs should be collected, as much as possible, every 4-6 hours (± 30 minutes) after the first dose during the treatment period, 24 hours (± 2 hours) post final dose, and then once a day until discharge.

Study drug infusions should occur every 6 hours (± 30 minutes).

All assessments that are scheduled for every 24 hours or ≥ 24 hours post dose should occur within 2 hours of the scheduled time point, as much as possible, except for the 24-hour postpartum assessments which have a window of ± 6 hours.

The 6-week follow-up visit/phone call should be conducted 6 weeks (± 1 week) postpartum.

For infants, corrected gestational age is based on gestational age determined at time of consent. Thirty-six week corrected gestational age assessments for infants should be conducted at 36 weeks (± 1 week) corrected gestational age.

In all cases, the actual time of sample collection or assessment completion will be recorded on the subject's CRF.

Missed samples or breakage of a sample must be recorded on a sample inventory list and as a comment on the subject's CRF.

If clinically appropriate, blood samples collected for analysis of AMAG-423 PK may be drawn from a central line, by venipuncture, or by placement of a peripheral catheter.

For instances where assessment times correlate with study drug dosing times, all assessments should be completed prior to start of dosing.

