6.4.5 Data Safety Monitoring Board

An independent Data Safety Monitoring Board (DSMB) will be initiated by the Sponsor. The DSMB will be comprised of a chairperson with significant DSMB experience as a chairperson, and two physicians with expertise in Maternal and Fetal Medicine or Neonatology and clinical trial conduct. A DSMB charter approved by the DSMB members will outline the responsibility of the DSMB. The safety of AMAG-423 will be assessed based on AEs, vital signs (including blood pressure, heart rate, respiratory rate, temperature, and pulse oximetry), and clinical laboratory tests. The DSMB will convene prior to dosing of the first subject to determine if additional data will be needed at each review. At the initial meeting, the DSMB will determine frequency of meetings and whether meetings will be based on enrollment or be regularly scheduled calendar events.. The timing of the DSMB reviews and scope of the safety review will be detailed in the DSMB Charter. The DSMB will have authority to stop the study based on safety concerns or to require implementation of new safety assessments as appropriate.

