- Fetal heart rate monitoring – 24-hour continuous fetal heart rate monitoring (to be initiated at start of first dose) until 24 hours post first dose. For the remainder of the treatment period, continuous fetal heart rate monitoring should be conducted for one hour after initiation of each dose, unless additional fetal heart rate monitoring is clinically indicated. Clinically significant abnormal findings along with category designation (e.g., III) from fetal heart rate monitoring must be recorded. If continuous fetal heart rate monitoring is difficult or not possible due to subject's weight and/or fetal gestational age, attempts to obtain several one hour strips on Day 1 of treatment should be made documenting why continuous fetal heart rate monitoring is not possible.
- Biophysical profile – completed per standard of care.
- Laboratory assessments (clinical chemistry, hematology, and urinalysis), including serum creatinine – should be collected 24 hours after the first dose (± 2 hours) and then per standard of care, and/or minimally, once a day. As much as possible, labs should be collected 24 hours apart.
 - Urinalysis conducted 24 hours after the first dose should include electrolytes, as much as possible, and then SOC. See [Appendix 3](#).

- A full set of vital signs (i.e., blood pressure and heart rate, respiratory rate, body temperature, and pulse oximetry) – should be collected every 4-6 hours after first dose, as much as possible.
- Preeclampsia symptom assessment – should be collected per standard of care, and/or minimally, once a day, starting approximately 24 hours after the first dose. See [Appendix 4](#).
- MEOWS – should be conducted 24 hours after the first dose (± 2 hours) and then once a day. As much as possible, MEOWS should be completed 24 hours apart. See [Appendix 5](#).
- Adverse event record
- Concomitant medication record
- AMAG-423 PK blood sample collection and blood sample collection for assay development per the following table, as much as possible:

Dosing time (hour administered)	Sample Time			
	Pre-dose	End of infusion**	3 hours post dose	6 hours post dose
0	X*	X	X	X
24	X	X		
90***	X	X	X	X

*One sample collected as soon as possible after consent and a second sample just prior to dosing for assay development. One sample collected for AMAG-423 PK analysis.

**End of infusion samples should be obtained at or just prior to stopping the infusion pump

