8.9 Adverse Events

An adverse event is defined as any untoward medical occurrence associated with use of a drug in humans, whether or not considered drug related. It can be any unfavorable and unintended sign (including laboratory values), symptom or disease temporally associated with use of the study treatment, whether or not it is associated with investigational treatment.

For purposes of this study, symptoms/sequelae of preeclampsia/eclampsia, symptoms of pregnancy and childbirth, and conditions related to prematurity are not considered adverse events unless they are unexpected or are significantly worse than would normally be expected ([Appendix 4](#)) in the opinion of the Investigator.

All AEs reported by the subject or observed will be recorded. Serious adverse events (SAEs) should be reported to the sponsor by telephone or fax within 24 hours of learning of their occurrence. Non-serious adverse event data will be recorded in each subject's CRF and submitted to the sponsor for review on an ongoing basis in conjunction with interim Sponsor monitoring visits.

Adverse event collection begins from the time of Informed Consent and continues throughout the study, until 6 weeks postpartum for the mother, and for the infant until 36 weeks (\pm 1 week) corrected gestational age. A separate AE record will be maintained for mothers and infants. Mothers will be questioned about their general health in conjunction with vital sign assessments. The question should be of a general nature and should not suggest symptoms to the subject (e.g., "How are you feeling?" rather than "Do you have a headache?"). If an AE is reported or observed, the site staff should follow the initial question with clinical evaluations and additional questions aimed at obtaining additional details about the AE.

When adverse events are observed or reported, whether in response to indirect questioning or volunteered by subjects, all relevant evaluations will be completed and appropriate treatment provided, if necessary. Subjects with adverse events should be followed until the Investigator and Sponsor consider the event to have resolved, stabilized, or no longer require follow-up for study purposes.

In order to avoid vague, ambiguous, or colloquial expressions, the adverse event should be recorded in the CRF using standard medical terminology rather than the subject's own words.

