9.7 Analysis of Safety Data

Safety data as outlined in [Section 8](#) will be summarized by treatment group for both mothers and infants. Summary statistics will be prepared for measured values and changes from baseline values for each dose group. No statistical inference testing will be performed on the safety data.

Adverse events will be coded using the Medical Dictionary for Regulatory Activities (MedDRA) coding dictionary and summarized by relatedness, intensity, and seriousness. AEs may also be summarized by other factors such as gestational age or intensity of baseline preeclampsia symptoms. Summaries of the adverse event data will be completed for all subjects. Summaries of the number and percentage of subjects with at least one treatment emergent AE, classified according to preferred term and/or body system using the MedDRA dictionary, will be provided overall and by treatment group for:

- Overall summary
- All treatment-emergent AEs
- Treatment-emergent AEs by relationship (probably not related, possibly related, probably related)
- Treatment-emergent AEs by intensity (mild, moderate, severe)
- SAEs
- Treatment-emergent AEs leading to withdrawal from the study

Heart rate, systolic and diastolic blood pressure, temperature, respiratory rate, and pulse oximetry versus time data will be summarized by treatment group with descriptive statistics at each scheduled time point. Individual and mean values versus time profiles will be provided for each treatment group. Summaries of treatment-emergent clinically important abnormalities in vital sign and laboratory data will be provided. No inferential statistical analysis is planned.

Clinically significant new abnormal findings of vital signs or clinical laboratories will be reported as adverse events.

Laboratory parameters, vital sign data, and weight will be summarized by treatment group and presented in tabular and graphic formats where appropriate. Appropriate cross-tabulations will be provided to detect any significant changes in laboratory parameters, vital sign values, or weight but no formal statistical tests are planned.

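### No maternal vital-sign set or prompted adverse-event question is required during or soon after an infusion, so the by-arm vital-sign tables cannot support a statement of no acute maternal effect

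*Combined protocol and SAP*

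**What the plan says.** Section 6.4.3 plans 16 doses over up to 90 hours, and Section 7.7 spaces them 6 hours apart with a window of ±30 minutes. Section 6.4.8 has each infusion last at least 30 minutes.

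Maternal vital signs are taken within the hour before the first dose (Section 7.2). After that, Section 7.7 has them collected, as far as possible, "every 4-6 hours (± 30 minutes) after the first dose during the treatment period". The same section sets the order when an assessment and a dose fall together: "For instances where assessment times correlate with study drug dosing times, all assessments should be completed prior to start of dosing".

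Section 8.9 attaches the routine adverse-event question to these sets: "Mothers will be questioned about their general health in conjunction with vital sign assessments". In the analysis (Section 9.7), heart rate, blood pressure, temperature, respiratory rate and pulse oximetry "versus time data will be summarized by treatment group with descriptive statistics at each scheduled time point". For the DSMB, Section 6.4.5 says: "The safety of AMAG-423 will be assessed based on AEs, vital signs" and laboratory tests.

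The fetus is monitored after dosing. Monitoring is continuous for the first 24 hours, and for the rest of the treatment period "continuous fetal heart rate monitoring should be conducted for one hour after initiation of each dose" (Section 7.3). There is no maternal counterpart.

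**The concern.** A by-arm table of vital signs is informative about acute effects only if it contains values from the period in which such effects would appear. Here the collection interval is close to the dosing interval, and readings that coincide with a dose come before it. Many of the tabulated values, and on one permitted schedule all of them, are therefore end-of-interval values. A flat table could be read as evidence of no acute maternal effect when it could hardly have shown one.

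Maternal safety is the first secondary objective. Exclusion criterion 11 is explained by possible allergic reactions to DIF. In Protocol 01, the reported difference in mean arterial pressure was seen over the first 4 hours of treatment. Earlier antepartum experience (the DEEP study) covers 24 women given a different DIF product at 1.6 mg/kg for 48 hours; this trial gives 3.2 mg/kg for up to 90 hours.

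**Working it through.** **Inputs.** Doses every 6 h ±0.5 h (7.7); 16 doses (6.4.3); vital signs every 4 to 6 h ±0.5 h, counted from the first dose (7.7); a coincident set is taken before the dose (7.7).

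**The plan's own frame.** (16 − 1) × 6 = 90 h for the last dose, and 90 + 6 = 96 h for the treatment period. Both agree with Sections 6.4.3 and 7.3.

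**After dose 1.** The earliest set is due at 4 − 0.5 = 3.5 h and the latest at 6 + 0.5 = 6.5 h. This gap comes from the interval alone; the ordering rule plays no part in it.

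**All doses.** Put doses at 0, 6, ..., 90 h and sets at multiples of 4, 5 or 6 h up to 96 h. Measure each set from the start of the previous infusion.

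| Interval | Sets | Coincide with a dose | Hours since previous dose (number of sets) | Doses with a set within 1 h | Doses with a set within 2 h |
|---|---|---|---|---|---|
| 4-hourly | 24 | 7 | 2 (8), 4 (8), 6 (8) | 0 of 16 | 8 of 16 |
| 5-hourly | 19 | 3 | 1 (3), 2 (3), 3 (3), 4 (3), 5 (4), 6 (3) | 3 of 16 | 6 of 16 |
| 6-hourly | 16 | 15 | 6 (16) | 0 of 16 | 0 of 16 |

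**Using the windows.** The shortest possible gap takes the dose as late and the set as early as allowed, which subtracts 0.5 + 0.5 = 1 h from the shortest nominal gap:
- 6-hourly: 6 − 1 = 5 h (5.5 h if the set's window is counted from the actual previous dose)
- 4-hourly: 2 − 1 = 1 h
- 5-hourly: 1 − 1 = 0 h

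At nominal times, none of these three schedules puts a set inside a 30-minute infusion.

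**Other scheduled contacts.**
- MEOWS includes blood pressure, heart rate, respiratory rate and oxygen need. It is due 24 h after the first dose (±2 h) and then daily. The 24-hour point coincides with a dose, so the ordering rule places it before that infusion.
- PK draws are due at the end of infusion for the 0-hour, 24-hour and last doses, and 3 h after the 0-hour and last doses. They bring staff to the bedside, but no vital signs are required.
- Fetal heart rate monitoring supplies no maternal values.
- Standard-of-care readings are captured only when there is a clinical finding (7.3), so more frequent ward checks do not yield by-arm data.

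**The case against.** The strongest reply is that real reactions are covered by other routes. Adverse events that are volunteered or observed are recorded (8.9). New clinically significant vital-sign findings become adverse events, and treatment-emergent events are tabulated by arm and by preferred term or body system (9.7). The women are inpatients in tertiary or quaternary centres, and unscheduled assessments are allowed (7.1). The DSMB can ask for further data and require new safety assessments (6.4.5). All of this stands. A reader might infer that infusion reactions will go unrecorded; the documents do not support that, and severe reactions should be caught.

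A reader might also infer that all maternal vital signs are taken before dosing, or that Section 7.7 bars post-infusion checks. Neither holds. The ordering rule touches only coincident sets: 15 of 16 on a 6-hourly schedule, but 3 of 19 on a 5-hourly one and 7 of 24 on a 4-hourly one. The same section sets windows for end-of-infusion and 3-hour PK draws, so it plainly allows procedures after dosing.

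The background evidence is also limited. Protocol 01 was postpartum, used Digibind, and reported lower pressure as an intended effect. Exclusion 11 reduces the allergy risk and does not show a monitoring gap. DIF was well tolerated in DEEP. These facts show only why the early hours are worth measuring.

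What the reply leaves open is scheduled measurement of milder acute changes. Actual assessment times are recorded in the CRF, so time since dosing can largely be derived for sets that exist, but values that were never collected cannot be recovered at analysis.

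**Conclusion.** The concern holds as a minor gap in data collection. No maternal vital signs or prompted question are required during or soon after any infusion. None is due in the first 3.5 hours after dose 1, and on a 6-hourly schedule none within the 5 hours after any dose. On 4- and 5-hourly schedules, 8 and 6 of 16 doses respectively have a set within a nominal 2 hours. The Section 9.7 tables and the DSMB's vital-sign data will therefore hold few or no early post-infusion values, and a null result in them should not be reported as absence of an acute maternal effect.

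The counts assume a fixed interval at each site, a full course of 16 doses, and windows set around nominal clock times; repeated drift could shorten the 5-hour figure. The documents do not say which interval sites use. They also give no rate or time course of reactions, so the size of any missed effect cannot be computed. No primary or key secondary conclusion is affected.

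**What to change.** In Sections 7.3 and 7.7, add blood pressure, heart rate, respiratory rate, SpO2 and the general adverse-event question, in both arms, at PK draws already scheduled:
- end of infusion for the 0-hour, 24-hour and last doses
- 3 hours after the 0-hour and last doses

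In Section 9.7, summarise the change from the pre-dose value at these points by arm, descriptively and apart from the routine series. Take the pre-dose value as the last set before that infusion, because a 5-hourly schedule has no set at 24 h and a 4-hourly one has none at 90 h. Provide the same summary to the DSMB. No special MedDRA grouping is needed, since Section 9.7 already tabulates events by preferred term or body system.

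The cost is 3 + 2 = 5 short sets per woman, so at most 5 × 200 = 1,000 in total, plus some CRF fields and one table. No new bedside visit or blood draw is needed. More minor events will be recorded in both arms, and women who deliver early will contribute fewer sets.
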